
Follow-Up: As part of standard of care, subjects will be seen every 4-6 weeks during their regularly scheduled weight management appointments to assess height, weight, and to calculate BMI. The subject will meet with a dietitian for further guidance and recommendations at baseline and the end of the study (approx. 3 months) and will meet with the physician for a routine exam at each visit as per standard of care in our pediatric weight management program. In addition to standard of care, at each visit subjects will complete the questionnaire as described above. Branching logic will be used within REDCap to direct appropriate questions to subjects with or without the PHC. The questionnaire is designed to assess compliance (see measures section). A separate survey will be used at the final visit; however the same survey procedures will be followed. During the 3 month study window we expect up

to 4 time points (baseline, months 1, 2 and 3(the final visit). If visits do not fall every 4 weeks, then fewer interim data points will be collected.

Measures: We will gather data from a variety of sources including EMR documentation (for standard of care visits) as well as subject surveys.

Exposure: Using the two-single arm study design, we will compare Kurbo vs. our known standard and Kurbo + PHC vs our known standard. Our standard of care estimates are based on existing data from a 6 month Baystate pediatric weight management spinoff called MIGHTY. Both MIGHTY and Kurbo could be considered augmented programs that spin off of our pediatric weight management program. MIGHTY stands for Moving, Improving, and Gaining Health Together at the YMCA. It is an intensive six-month group program that emphasizes physical activity, nutrition, and change of habits for the entire family. It includes a fitness evaluation, individual fitness prescriptions, group exercise sessions, individual and group nutritional counseling as well as strategies for maintaining lifelong health. Families who participate in MIGHTY receive a free six-month membership to the Springfield YMCA. Children interested in enrolling in MIGHTY must first be evaluated through our Pediatric Weight Management Program. Estimates from this program will be adapted for our power calculations.

If we can establish that Kurbo is better than our known standards, then we will estimate differences between Kurbo vs. Kurbo + PHC. Group assignment will be randomized in a 1:1 ratio using random permuted blocks.

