A Pilot Study to Assess the Compliance and Impact on Weight of Kurbo, a Pediatric Centered Weight Loss App
Clinical Trials ID NCT02880254
Outcomes

Compliance: The compliance measure from our known standard (MIGHTY program) is showing up for a visit (e.g. attendance). As comparable measures, we will define compliance with Kurbo app to be daily use for tracking food intake, exercise, accessing the app features (games, badges). Surveys will have specific questions such as: "Over the last month, how many days per week do you usually use Kurbo to track food?" A summary compliance score will be calculated as follows: we expect subjects to use Kurbo to track food daily (7 days per week). Over the 3 follow-up study visits, if a subject responds to the above question with a 7, 5 and 6, we will take the average of this and divide it by the expected. In the above example: $18/3 = 6$ and $6 / 7 = 85.7\%$ compliant. Expected compliance for using Kurbo to track exercise = 7 days. There is no expected compliance for the use of games and obtaining badges.

Compliance with the PHC will be assessed based on the subjects' ability to have these meetings at least once a week. In order to collect this information we will ask "Over the last month, how many total meetings have you had with your personal health coach?" Compliance will be assessed in the same way as defined above with the expected compliance of 4 times in the last month. Use of the coaching feature will be defined as a complete phone or video conference. We will also assess the number of times they needed to reschedule these PHC visits.

BMI-z score: This is standard of care data that is recorded in PEDRO. The research coordinator will gather relevant BMI-z score data from PEDRO and enter it into REDCap for all study visits.

Covariates: We will collect the following from the EMR (age (yr, mo), height (cm), weight (kg), insurance category (private vs public), sex, race, and ethnicity). We will also ask subjects what their current grade level is.

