To assess our hypotheses we will utilize one-sample tests with a one-sided alpha of 0.025. One-sided tests will be used as we are only interested in whether the use of this app results in better outcomes than usual care. Compliance will utilize a binomial probability test to assess compliance (calculated over 3 months) against our known compliance of 50%. BMI-z score change (absolute change from baseline to 3 months) will utilize a one-sample t-test to assess observed BMI-z score change at 3 months against our estimated change of a 1% decrease. We will present our findings graphically, along with point estimates and one-sided 97.5% confidence intervals.

Assuming we find improved compliance and BMI-z scores, we will also estimate compliance and BMI-z score differences between Kurbo and Kurbo + PHC. Estimates will be generated using direct observation as well as prediction through modeling (e.g. GEE, linear mixed models). As data will be collected monthly, we will also describe changes over time and any possible dose-response effects. We will also evaluate possible differences in effects based on age category stratification (10-14 yrs and 15-17 yrs). We will present our findings graphically, along with 95% confidence intervals. These results may be used to inform study design and power calculations for a future study assessing differences between Kurbo and Kurbo + PHC as well as changes in obesity-related comorbidities.

Power and Sample Size: Studies in pediatric and adult weight management trials indicate that the attrition rate is poor (4, 6, 8) as well as unpublished data from our pediatric weight management spin off program, MIGHTY, indicate that 6 month compliance (attendance) is close to 50% and 6 month change in BMI-z scores is approximately a 2% decrease with a change standard deviation (SD) of 0.12. As described in our data analysis section, we will estimate compliance to be 50% and BMI-z decrease 1%. We will keep the same SD of 0.12. Sample size calculations assume a one-sided alpha of 0.025, and power of 0.80.

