In regards to compliance, we feel that to be of clinical importance we would want to observe close to 75% compliance with the Kurbo app and/or Kurbo + PHC. With a sample of 30 subjects in each Kurbo group (60 total), we would be able to conduct a one-sided, one-sample test against 50% compliance if we observe at least 75% compliance in our study groups (a 25% improvement in compliance). Larger samples would be required to test a smaller effect size (e.g. nearly 50 subjects per group would be required to test 70% compliance against 50%) and with the same sample size power would drop to 0.59 to test a 20% difference.

In regards to BMI-z score change, we feel that to be clinically relevant we would want to observe at least a 5% decrease (BMI-z score at baseline=2.267 vs. 3 months=2.154) in BMI-z score over a 3 month period

with the Kurbo app and/or Kurbo + PHC. With a sample of 12 subjects in each group, we would be able to conduct a one-sided, one-sample t-test against a 1% decrease assuming a standard deviation of 0.12 if we observe at least a 5% decrease in BMI-z score in our study groups. Effect sizes greater than the 4% difference described above will be picked up by this sample size. However, in the case that we have underestimated the SD, the upper limit of the 95% confidence interval is 0.14. With this SD we would need 19 subjects to detect this same effect.

If we progress to a comparison between Kurbo vs. Kurbo + PHC, we will utilize a repeated measures model such as GEE or linear mixed models. As we have no preliminary estimates of variability or correlation over time, we have estimated the sample required for a medium effect size of 0.50 (Cohen's d, calculated as the difference between means divided by the pooled standard deviation) assuming a two-sided alpha of 0.05, power of 0.80 and 4 repeated measures with a correlation of 0.3. In this case, we would need to sample balanced groups of approximately 28 each. If the correlation increases (e.g. 0.5 or 0.7) power will increase.

Based on the above information, in addition to adding ~20% for possible study withdrawal, we wish to recruit a total of 35 subjects in each Kurbo group for a total sample size of 70 subjects. This sample size should allow us to assess clinically relevant outcomes with sufficient power.

A Pilot Study to Assess the Compliance and Impact on Weight of Kurbo, a Pediatric Centered Weight

Loss App

Clinical Trials ID NCT02880254

Risks and Benefits

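### The primary compliance score comes only from surveys at attended visits, with no analysis set or missed-survey rule, while its 50% benchmark is attendance itself; this tilts the primary test towards success

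*Combined protocol and SAP*

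**What the plan says.** **How the data arise.** Under Randomization, Allocation and Blinding, the coordinator opens the survey on a clinic computer during a scheduled visit. Follow-Up has it completed at each visit, and visits fall every 4 to 6 weeks. Measures names only the medical record and subject surveys as sources. No app usage log and no remote survey is described.

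**How the score is built.** Outcomes, Compliance, says of the monthly answers: "we will take the average of this and divide it by the expected". The one worked example has all three follow-up answers (7, 5 and 6, giving 85.7%). Coaching compliance is scored in the same way against four meetings a month.

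**What is said about missing answers.** Follow-Up notes: "If visits do not fall every 4 weeks, then fewer interim data points will be collected". It also says: "A separate survey will be used at the final visit". Power and Sample Size goes from 30 to 35 per group "in addition to adding ~20% for possible study withdrawal". No section says how a missed survey or a withdrawn child enters the score or the test, and no analysis population is defined.

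**The comparator.** MIGHTY compliance "is showing up for a visit (e.g. attendance"), put at close to 50% at six months and carried unchanged to three. Data Analysis plans a binomial test "to assess compliance (calculated over 3 months) against our known compliance of 50" per cent. In its words, "we will utilize one-sample tests with a one-sided alpha of 0.025".

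**The concern.** A child who stops coming to clinic stops producing compliance data. Averaging whatever answers exist scores that child on the early months only, and a child who never returns has no score. On the benchmark side the outcome is attendance, so not coming is itself the failure. The same behaviour can thus be missing data in the Kurbo groups and non-compliance in the standard they are tested against.

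Children who disengage are the ones a compliance endpoint most needs to count. Dropping them raises observed compliance in both groups. The plan itself describes attrition in weight management as poor, so the situation is expected. A favourable result on compliance and BMI-z also opens the comparison of Kurbo with Kurbo plus coach, and compliance is what the pilot is meant to tell a larger study.

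**Working it through.** **Inputs from the documents:** null 50%; target 75%; one-sided alpha 0.025; power 0.80; 30 evaluable and 35 enrolled per group; about 20% withdrawal.

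**Assumptions, not in the documents:** each child is classed as compliant or not (the binomial test needs this, but the protocol defines a percentage score with no cut-off); the loss rate where it is not 20%; and the share *c* of withdrawn children who are compliant.

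**1. The plan's own figures.** The exact binomial test rejects at the smallest r with P(X ≥ r | n, 0.5) ≤ 0.025. For n = 30, r = 21: size 0.0214, power 0.803 at 75% and 0.589 at 70%. The smallest n with 80% power is 30 for 75% and 49 for 70%. These agree with the stated 30, 0.59 and nearly 50, so the sample-size arithmetic for compliance is not in question.

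**2. Effect on one child's score.**

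| Answers | Mean of available answers ÷ 7 | Missed months as 0, divisor 3 |
|---|---|---|
| 7, missed, missed | 7/7 = 100% | 7/21 = 33.3% |
| 7, 5, missed | 6/7 = 85.7% | 12/21 = 57.1% |
| 7, 5, 6 (protocol example) | 85.7% | 85.7% |

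On available answers, the second child cannot be told apart from the protocol's complete case.

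**3. Effect on the test at 20% loss.** 35 × 0.80 = 28 scored; reject at r = 20; size 0.018. Let true compliance over all 35 be the null 50%. The rate among scored children is (0.50 − 0.20*c*)/0.80.

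| Withdrawn children compliant (*c*) | Rate among the 28 | P(reject) |
|---|---|---|
| 0% | 62.5% | 0.220 |
| 25% | 56.25% | 0.075 |
| 37.5% | 53.1% | 0.038 |
| 50% | 50.0% | 0.018 |

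**4. Other loss rates, with *c* = 0.** At 10% loss, 31 or 32 children remain (35 × 0.90 = 31.5) and the rate among them is 0.50/0.90 = 55.6%. P(reject) is 0.059 for n = 31 and 0.0445 for n = 32. At 30% loss, 24 remain, the rate is 71.4% and P(reject) is 0.449.

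**5. All randomised children counted.** n = 35, r = 24: size 0.0205 whatever the loss. Power is 0.858 if 75% of all 35 comply. If 75% holds only among attenders and leavers count as non-compliant:

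- 10% loss: 0.75 × 0.90 = 67.5% overall, power 0.53.
- 20% loss: 0.75 × 0.80 = 60.0% overall, power 0.20.

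**The case against.** **The plan is silent; it does not prescribe exclusion.** A reader might infer that the protocol instructs analysts to drop children who leave or to score them on their early answers. No sentence says so. The worked example divides by three with all answers present, which fits a fixed divisor equally well. The remark about fewer data points concerns visit spacing under a 4-to-6-week schedule, not dropout. The withdrawal allowance follows the compliance, BMI-z and repeated-measures calculations and is not specific to compliance. This stands: exclusion is inferred. The inference is still a strong one, because inflating for withdrawal serves its purpose only if withdrawn children are not counted.

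**The benchmark cannot be examined.** The MIGHTY data are unpublished. The documents do not say whether 50% is a share of sessions attended or of children still attending, or over what denominator. It is tempting to say that a given child who left would have been counted non-compliant in MIGHTY; the text does not establish that. It does establish that the benchmark is attendance, so missed visits pull it down.

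**22% is an extreme.** It requires every withdrawn child to be non-compliant. If withdrawn children comply at the same 50% as the rest, there is no inflation. This stands, and the range has to accompany the figure.

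**The final survey may contain the items.** A reader might conclude from the separate final-visit survey that the month-3 answer is missing. The instruments are not in the text, and the scoring rule refers to three follow-up visits, which implies that the question is asked. It needs confirming and is not a demonstrated fault.

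**Conclusion.** The concern holds as a gap in the primary analysis with a predictable direction of bias. Compliance is observed only in children who attend, no analysis set or missed-survey rule is given, the sample size implies that withdrawn children leave the test, and the comparator is attendance. Read that way, the plan favours rejecting the 50% null.

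At the plan's own 20% allowance, the chance of rejecting when compliance over all 35 is 50% runs from about 2% to 22%, depending on how many withdrawn children were compliant. At 10% loss with none compliant it is about 4.5% to 6%. These figures rest on a binary classification that the protocol does not define. The effect of scoring children on early answers alone is shown at score level only, since without a cut-off it cannot be carried to the test.

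The documents do not support saying that the plan mandates exclusion or that its false-positive rate is 22%. The gap should still be closed before data are seen, because the choice of rule can decide the primary result.

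**What to change.** - **Analysis set (Outcomes, Compliance; Data Analysis).** Make all randomised subjects the primary compliance set in each group.
- **Score.** Use a fixed divisor of three monthly values and enter 0 for any month missing through withdrawal or non-response.
- **Timing (Follow-Up).** Collect the same compliance items at weeks 4, 8 and 12, in clinic or by REDCap link when no visit falls then. Without this, a fully engaged child on six-weekly visits would have two answers and score at most 14/21 = 66.7%.
- **Final survey.** Confirm that it contains the compliance items.
- **Sensitivity analysis.** Report the answered-surveys-only score.
- **Power and Sample Size.** State that power of 0.858 with 35 per group assumes 75% compliance among all randomised children, and give the values if 75% holds only among attenders (about 0.53 at 10% loss and 0.20 at 20%).

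**Cost.** The change is mainly wording, plus survey links in a system already in use. Subjects' contact details, mentioned now only for Kurbo registration, would be needed for the links. Children who keep using the app but do not answer will be under-scored, and remote answers lose the private exam-room setting. Zero for non-response is one defensible choice among several and biases compliance downwards, so it should be stated as such. The power loss is the larger price: if many children leave, the test will often fail to reject. No extra subjects are needed only if the 75% target is meant for everyone randomised.

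### The coach-compliance score averages uncapped meeting counts over an undefined month, so it can exceed 100% and extra meetings can offset a month with none

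*Combined protocol and SAP*

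**What the plan says.** The primary aim (Primary Specific Aims & Hypotheses) is 3-month compliance with the app and with the app plus coach. The Compliance paragraphs under Outcomes define the coach part in three steps.

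- **Target:** "Compliance with the PHC will be assessed based on the subjects' ability to have these meetings at least once a week". A meeting counts if it is a completed phone or video conference.
- **Survey item:** "Over the last month, how many total meetings have you had with your personal health coach".
- **Score:** "Compliance will be assessed in the same way as defined above with the expected compliance of 4 times in the last month".

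The rule it refers back to is the food-tracking rule. Responses from the follow-up visits are collected and "we will take the average of this and divide it by the expected". The food item itself asks "Over the last month, how many days per week do you usually use Kurbo to track food", with 7 as the expected value.

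On timing, the Follow-Up section says "subjects will be seen every 4-6 weeks during their regularly scheduled weight management appointments". It expects time points at baseline and months 1, 2 and 3, and adds: "If visits do not fall every 4 weeks, then fewer interim data points will be collected". The plan gives no length for the recall month, no upper limit on the meeting count, and no minimum for any single week or month.

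**The concern.** The rule was written for an answer that is bounded by construction and then carried over to one that is not. A child cannot track food on more than 7 days a week, so a poor month always pulls the food score down and no other month can make up for it. Coach meetings are an open count, and a target of at least one a week allows more. Averaging before any limit is applied lets a busy month pay for an empty one.

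The numerator and denominator may also cover different periods. The target is weekly and the expected count is 4, but the question asks about a month. If children answer for a calendar month, 4 is slightly fewer than the number of weeks covered.

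What is at stake is how the compliance result can be read. The pilot is meant to establish feasibility for a larger study (Prior Studies and Feasibility). Falling contact with the coach over three months is something such a pilot should reveal, and this score can hide it.

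**Working it through.** **Inputs.** All are from the Compliance paragraphs under Outcomes unless noted: weekly target; total meetings per report; expected count 4; mean of responses divided by expected; up to three follow-up reports (Follow-Up). The length of a month is not given. I assume 365.25/12 = 30.44 days and show 28 to 31 days.

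**1. The plan's own example.** Score = mean(responses) / expected. For food responses 7, 5 and 6: (7 + 5 + 6)/3 = 6, and 6/7 = 85.7%. This matches the plan, so how the rule runs is not in doubt.

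**2. The same rule for coach meetings.** Score = mean(counts) / 4. The capped column replaces each count above 4 by 4 before averaging.

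| Reports | As written | Each report capped at 4 |
|---|---|---|
| 4, 4, 4 | 12/3/4 = 100% | 100% |
| 8, 4, 0 | 12/3/4 = 100% | (4+4+0)/3/4 = 66.7% |
| 6, 6, 0 | 12/3/4 = 100% | (4+4+0)/3/4 = 66.7% |
| 12, 0, 0 | 12/3/4 = 100% | (4+0+0)/3/4 = 33.3% |
| 5, 5, 0 | 10/3/4 = 83.3% | (4+4+0)/3/4 = 66.7% |
| 5, 4, 4 | 13/3/4 = 108.3% | 100% |
| 8, 0 (two reports only) | 8/2/4 = 100% | (4+0)/2/4 = 50% |

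For comparison, the best food score with one empty month is (7 + 7 + 0)/3/7 = 66.7%. Capping only the final average would remove scores above 100% but leave 8, 4, 0 at 100%, so the cap has to act on each report. None of this depends on the length of a month.

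**3. Length of the month.** For exactly one meeting a week, score = (days/7)/4.

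- 28 days: 4.00/4 = 100%
- 30 days: 4.286/4 = 107.1%
- 30.44 days: 4.348/4 = 108.7%
- 31 days: 4.429/4 = 110.7%

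**4. Sample size.** The compliance calculation in Power and Sample Size does not use the coach score. With 30 per group, a 50% null and success at 21 or more, the exact one-sided alpha is 0.0214. Power is 0.803 at 75% and 0.589 at 70%, against the stated 0.80 and 0.59. The scoring problem leaves these figures unchanged.

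**The case against.** **The month may simply mean 4 weeks.** Follow-Up links months 1, 2 and 3 to 4-weekly visits, and setting a weekly target equal to 4 meetings is exact on that reading. Weekly attendance then scores 100% and there is no inflation. This stands: a reader might infer from the calendar-month arithmetic that the score is biased upward by about 9%, but the documents do not establish that. What remains is that the survey question does not tell the child which period is meant.

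**Cumulative attendance is a legitimate summary.** Data Analysis says compliance is calculated over 3 months, and 12 meetings against 12 expected is a fair measure of total coach contact. That is true as a measure of dose. It is not a measure of the stated target, "ability to have these meetings at least once a week", which a child with an empty month has missed.

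**The offsetting patterns are hypothetical.** This also stands. The documents do not say how often a child can book or would attend more than one meeting a week, so the frequency is unknown.

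**Other steps would reveal it.** Data Analysis plans outlier inspection, logic checks, medians and ranges, and a description of change over time. A count of 12 would probably be noticed; a count of 6 might not. The description over time is planned only if compliance and BMI-z improve. None of these steps changes how the score is computed.

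**A monthly cap does not enforce a weekly target.** Four meetings in one week and none in the next three would still score 100%. This is correct and is the reason for the second option in the fix.

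**Conclusion.** The point holds as a scoring defect of minor weight. As written, the coach score can exceed 100%, and it can rate a child with a whole month without coach contact as fully compliant: 100% for 8, 4, 0 or 6, 6, 0, against 66.7% with each report capped. This follows from the stated rule and needs no assumption. The undefined month is a second, conditional issue: exact weekly attendance scores 100% if the month is 4 weeks and about 109% if it is a calendar month, with a range of 100% to 111%.

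A reader might go further and infer that the primary compliance test is tilted towards success. The documents do not support that. They do not say whether the coach percentage enters the binomial test against 50%, or how a percentage becomes a yes/no outcome for that test, so no effect on it can be computed. What can be said is narrower: compared with a capped 4-week score, the rule as written can only give an equal or higher value for the same child. Sample size and power are not affected.

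**What to change.** Either of two changes to the coach item and its score would do:

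1. Ask for the total number of completed coach meetings in the last 4 weeks, cap each report at 4, average the reports, and divide by 4.
2. Closer to the target: ask in how many of the last 4 weeks at least one coach meeting was completed, average the reports, and divide by 4. The answer is bounded at 4, as the food item is at 7, and meetings bunched in one week no longer count as several weeks.

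If total contact with the coach is also of interest, for example for the planned dose-response description, report the uncapped count as a separate descriptive measure.

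The cost is one survey phrase and one line in the score definition. Reported coach compliance may be slightly lower, and the score no longer credits extra meetings. With visits 4-6 weeks apart, a 4-week window leaves up to 6 - 4 = 2 weeks per interval unmeasured. A calendar-month question already leaves up to 6 - 4.35 = 1.65 weeks, so little extra coverage is lost.

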Study Timeline: We plan to recruit 70 subjects within the first 6 months of protocol acceptance. With nearly 22 new patients a week we do not anticipate that recruitment will take longer than 2 months, however we will leave our recruitment window open for 6 months at which time we will close recruitment, even if we have not accrued 70 subjects. As the Kurbo intervention is 3 months in duration, we expect the full implementation of this study to last approximately 9 months. Data analysis will be initiated by the EBRC at the completion of data collection. We anticipate analysis to take 3 months.

Prior Studies and Feasibility: As this is a pilot study, no preliminary studies have been conducted in support of this study. We anticipate timely recruitment given the high volume of new patients in our weight management clinic. In order to establish feasibility for a larger study, we will measure participant compliance and other feasibility measures with this pilot study.

The Principal Investigator has experience in conducting retrospective trials, drug treatment trials, prospective and randomized controlled trials during her time at Baystate as well as during her fellowship. Other members of the team, including the research coordinator and other providers, have also had some research experience in retrospective and prospective randomized controlled trials.

Data Analysis: We wish to evaluate two outcomes (compliance and BMI-z score change) among two groups (Kurbo and Kurbo + PHC). To do this we will use two single arm studies, where subjects will be randomized into either group, however each will be compared to a known standard. In this case, the known standards (based on existing data from our usual care group) are based on a 6-month compliance rate of 50% and a BMI-z score decrease near 2% (BMI-z score at baseline=2.27 vs. 6 months=2.22). To adapt these to a 3-month intervention, we feel that compliance at 3 months will remain the same (50%) and BMI-z change will be around 1% (BMI-z score at baseline=2.27 vs. 3 months=2.25).

Upon completion of the study, data will be inspected for outliers and logic checks will be conducted. Initial results will include means, standard deviations, medians and ranges for continuous measures and frequencies and percentages for categorical measures. Graphical representations will be utilized as needed.

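### The primary compliance test needs a yes/no outcome that the plan never defines, and sets app use against an assumed 50% attendance figure from MIGHTY

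*Combined protocol and SAP*

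**What the plan says.** **The test.** Data Analysis specifies a one-sample binomial test, one-sided alpha 0.025, to "assess compliance (calculated over 3 months) against our known compliance of 50"%. Power and Sample Size sets 30 subjects per group to detect 75% against 50%.

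**The score.** Under Outcomes, Compliance, subjects report at follow-up visits how many days a week they track food; "we will take the average of this and divide it by the expected" 7 days. The worked example gives 85.7%. Exercise tracking also has an expected 7 days, and coach meetings an expected 4 per month.

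**The benchmark.** The same section states: "The compliance measure from our known standard (MIGHTY program) is showing up for a visit (e.g. attendance"). Power and Sample Size says unpublished MIGHTY data show that "6 month compliance (attendance) is close to 50"%. Data Analysis carries this to 3 months: "we feel that compliance at 3 months will remain the same (50"%).

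**The comparator's name.** Data Analysis says "the known standards (based on existing data from our usual care group) are based on a 6-month compliance rate of 50"%. Hypothesis 1a likewise names the standard-of-care group, and the one-sided test is justified by reference to usual care. Exposure says the estimates come from MIGHTY, an intensive six-month group program, and adds: "Both MIGHTY and Kurbo could be considered augmented programs that spin off of our pediatric weight management program".

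**The concern.** Two things do not fit together.

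First, the outcome does not fit the test. A binomial test counts subjects who succeed. The plan gives each subject a continuous percentage, does not say which value counts as compliant, and does not say which score (food, exercise or coach) is the primary one in each arm. Until that is settled the primary test cannot be run as written, and the choice could be made after the data are seen.

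Second, the benchmark does not fit the claim. The 50% is a rounded estimate, from another time point, of another behaviour, in a program that the plan itself calls augmented. Both randomised arms receive Kurbo, so nothing inside the trial can check it.

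At stake is the primary conclusion. The result also helps decide whether the two Kurbo groups are compared, although that comparison is planned as descriptive.

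**Working it through.** **1. The plan's own figures.** Inputs from Power and Sample Size: one-sided alpha 0.025, power 0.80, null 0.50, alternative 0.75. With X the number of compliant subjects out of n, take the smallest r with P(X ≥ r | n, 0.50) ≤ 0.025; power is P(X ≥ r | n, p1).
- n=30: r=21, exact alpha 0.0214, power at 0.75 = 0.803. The stated 30 reproduces.
- n=30, p1=0.70: power 0.589 (stated 0.59).
- p1=0.70: smallest n with power 0.80 is 49 (stated as nearly 50).

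These match when each subject is one yes/no trial, so the calculation assumes a dichotomy that the outcome section does not supply.

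**2. What the missing cut-off does.** 4/7 = 57.1%; 5/7 = 71.4%. If every subject in an arm averaged 4 days, the mean score would be 57.1%, but the share compliant would be 100% at a 50% cut-off and 0% at 5 of 7. The 75% target has the same ambiguity. Read as a mean score it is 0.75 × 7 = 5.25 days a week; read as in step 1 it is the share of subjects above an unnamed threshold.

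**3. If the true 3-month standard is not 50%.** Illustration only, assuming one yes/no result per subject, n=30 and a pass at 21 or more. The chance that an arm merely equal to the standard passes is P(X ≥ 21 | 30, p):

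| True standard p | Chance of passing |
|---|---|
| 45% | 0.005 |
| 50% | 0.021 |
| 55% | 0.069 |
| 60% | 0.176 |

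**4. Sampling error in the 50%.** The plan gives no sample size for it, but it does allow for error in the MIGHTY SD of 0.12: "in the case that we have underestimated the SD, the upper limit of the 95% confidence interval is 0.14". Assume a two-sided chi-square limit, SD × √[(m−1)/χ²(0.025, m−1)]. At m=95 this is 0.12 × √(94/69.07) = 0.140, so about 95 children (46 to 350 if both figures are rounded). Assume further that the 50% is a yes/no rate in the same children. Averaging step 3 over a Beta(m/2, m/2) distribution centred on 50% gives 0.038 at m=95, 0.057 at m=46 and 0.026 at m=350, against 0.021 with no uncertainty.

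**5. What the planned confidence limit already shows.** The one-sided 97.5% exact lower limit for k of 30 is the 0.025 quantile of Beta(k, 31−k): 54.1% for k=22 and 57.7% for k=23. An observed result near the 75% target therefore beats 50% but not 60%.

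**The case against.** The strongest reply is that nothing is hidden. The plan states the carry-over as a judgement, calls the rate approximate and estimated, names both measures, and says the figures come from MIGHTY. A fixed historical benchmark is ordinary in a single-arm pilot. The planned one-sided limit lets a reader test other benchmarks, so formal tests at other values would add little. The follow-on comparison is descriptive, and Data Analysis makes it depend on improvement in both compliance and BMI-z score (Study Design allows either). All of this stands, and it limits the point. It does not supply a cut-off, make attendance and app use the same measure, or justify the words *known* and *standard of care* in the conclusion.

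A reader might go further in three ways that the documents do not support.
- *The benchmark favours Kurbo because attendance falls over time.* No month-3 MIGHTY value is given. If the 50% is a stable share of sessions attended, the carry-over does no harm. A true rate below 50%, or the demanding daily-use standard, would work against Kurbo.
- *The false-pass rate is several times nominal.* That needs a true standard well above 50%. Sampling error alone gives about 0.04 on the step 4 assumptions, and at a true 45% the rate is 0.005.
- *The sample size is wrong.* It reproduces.

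**Conclusion.** The point holds as a mismatch between test, outcome and benchmark. The firmest part is the missing cut-off and primary score: without them the stated test cannot be carried out, and the same subject can fall on either side. The second part limits the claim. A pass would show self-reported app use above an assumed 50%; it would not show compliance better than standard or usual care.

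The numerical effect of a wrong benchmark is illustrative. It rests on a yes/no outcome per subject, 30 analysed, and, for the averaged figure, an inferred MIGHTY sample of about 95. The effect of comparing attendance with app use cannot be quantified from the documents, and the net direction of bias is unknown.

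**What to change.** Settle the following before any outcome data are seen.

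1. **Score and cut-off.** Name the primary score for each arm: whether it is food tracking alone, and whether and how the coach score enters the Kurbo + PHC test. Set one per-subject cut-off for each score used, so that the binomial test and the 75% target both mean the share of subjects above it. Report neighbouring cut-offs as sensitivity analyses.
2. **Benchmark.** Use MIGHTY attendance through month 3, with its sample size and interval, if it was recorded. Otherwise keep 50% as the single benchmark, call it assumed throughout Data Analysis, and interpret the planned one-sided 97.5% limit against plausible values on both sides of 50%.
3. **Attendance.** Report Kurbo visit attendance beside app use. It is closer in kind to the MIGHTY measure but not like-for-like: Kurbo subjects are screened from their second clinic visit, and MIGHTY includes group sessions.
4. **Comparator.** Reconcile hypothesis 1a, Exposure, Data Analysis and Power and Sample Size so that hypothesis and conclusion refer to the MIGHTY benchmark.
5. **Missing data.** Report the test in all randomised subjects, with missing counted as non-compliant, and in available data, and state in advance which is primary. Visits never due because of 4-6 week spacing are not missing.

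**Cost.** Mostly wording, a record of which visits were due, and a look-up of MIGHTY records that may not hold month-3 values. The claim becomes narrower and results may look less favourable. Item 5 is a real trade-off, because a regular app user who misses a visit would be misclassified. With 35 randomised the pass mark is 24, and power is 0.86 if 75% of all 35 comply. If five withdraw and the other 30 comply at 75%, the all-randomised rate is 22.5/35 = 64% and power is P(X ≥ 24 | 30, 0.75) = 0.35, against 0.80 in available data. Those last two figures answer different questions, which is why the choice must be made in advance.
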